## Other Clinical Experience

Across 21 dose-ranging trials administering ipilimumab at doses of 0.1 to 20 mg/kg (n=2478), the following likely immune-mediated adverse reactions were also reported with less than 1% incidence: angiopathy, temporal arteritis, vasculitis, polymyalgia rheumatica, conjunctivitis, blepharitis, episcleritis, scleritis, iritis, leukocytoclastic vasculitis, erythema multiforme, psoriasis, arthritis, autoimmune thyroiditis, neurosensory hypoacusis, autoimmune central neuropathy (encephalitis), myositis, polymyositis, ocular myositis, hemolytic anemia, and nephritis.

## Embryo-fetal Toxicity

Based on its mechanism of action and data from animal studies, ipilimumab can cause fetal harm when administered to a pregnant woman. In animal reproduction studies, administration of ipilimumab to cynomolgus monkeys from the onset of organogenesis through delivery resulted in higher incidences of abortion, stillbirth, premature delivery (with corresponding lower birth weight), and higher incidences of infant mortality in a dose-related manner. The effects of ipilimumab are likely to be greater during the second and third trimesters of pregnancy. Advise pregnant women of the potential risk to a fetus. Advise females of reproductive potential to use effective contraception during treatment with a ipilimumab-containing regimen and for 3 months after the last dose of ipilimumab [see Use in Specific Populations (8.1, 8.3)].

## 4.3 Aspirin (Acetyl Salicylic Acid)

Aspirin used in this study will be commercial drug supply. Aspirin is to be stored as directed below.

### 4.3.1 Packaging and Labeling Information

Aspirin will be provided from a commercial supplier as tablets 325 mg size.

### 4.3.2 Clinical Supplies Disclosure

This trial is open-label; therefore, the subject, the trial site personnel, the Sponsor and/or designee are not blinded to treatment.

### 4.3.3 Storage and Handling Requirements

Clinical supplies must be stored in a secure, limited-access location at room temperature. Protect from light and freezing. Clinical supplies may not be used for any purpose other than that stated in the protocol. Receipt and dispensing of trial medication must be recorded by an authorized person at the trial site.

### 4.3.4 Returns and Reconciliation

Supplies will be tracked by the investigational pharmacist and dispensed directly to the patient.

### 4.3.5 Safety Information

Aspirin is associated with serious side effects including GI bleeding, renal side effects as well as platelet and bleeding abnormalities. The FDA has reviewed aspirin side effect and a comprehensive review is at <https://www.drugs.com/monograph/aspirin.html>.

## 5 Treatment Plan

### 5.1 Dosage and Administration

**Table 1 Regimen Description**

Drug	Dose/Potency	Dose Frequency	Route of Administration	Regimen/Treatment Period	Use
Pembrolizumab	200 mg	Q3W	IV infusion	Day 1 of each 3 week cycle	Experimental
Ipilimumab	1 mg/kg	Q3wk X4	IV infusion	Day 1 of each 3 wk cycle, for 4 cycles	experimental
Aspirin	975 mg	PO BID	oral	Each day	experimental

Trial treatment should begin on the day of randomization or as close as possible to the date on which treatment is allocated/assigned.

### 5.2 Timing of Dose Administration

Trial treatment should be administered on Day 1 of each cycle after all procedures/assessments have been completed as detailed on the Trial Flow Chart (Section 6.0). Trial treatment may be administered up to 3 days before or after the scheduled Day 1 of each cycle due to administrative reasons.

All trial treatments will be administered on an outpatient basis.

Pembrolizumab 200 mg will be administered as a 30 minute IV infusion every 3 weeks. Sites should make every effort to target infusion timing to be as close to 30 minutes as possible. However, given the variability of infusion pumps from site to site, a window of -5 minutes and +10 minutes is permitted (i.e., infusion time is 30 minutes: -5 min/+10 min).

Ipilimumab, 1 mg/kg will be administered for 4 cycles as a 60 minute intravenous infusion following the pembrolizumab. No premedication is used routinely. If any infusion reaction is suspected, the infusion may be stopped and antihistamines may be administered (Benadryl 50 mg PO or 25 mg IV) and the infusion restarted.

Aspirin, 975 mg PO Twice daily is taken orally by the patient. An adequate number of pills will be dispensed every 3 weeks and pill counts done to ensure compliance

### 5.3 Dose Modifications and Dosing Delays

Dosing interruptions are permitted in the case of medical / surgical events or logistical reasons not related to study therapy (e.g., elective surgery, unrelated medical events, patient vacation, and/or holidays). Subjects should be placed back on study therapy within 3 weeks of the scheduled interruption, unless otherwise discussed with the Sponsor. The reason for interruption should be documented in the patient's study record.

### **5.3.1 Dose Modification for Pembrolizumab**

Adverse events (both non-serious and serious) associated with pembrolizumab exposure may represent an immunologic etiology. These adverse events may occur shortly after the first dose or several months after the last dose of treatment. Pembrolizumab must be withheld for drug-related toxicities and severe or life-threatening AEs as per 3 below. See Section 5.6 for supportive care guidelines, including use of corticosteroids.

**Table 2 Pembrolizumab Dose Modification and Toxicity Management Guidelines for Immune-related AEs Associated with Pembrolizumab**

General instructions: 
 
1. Corticosteroid taper should be initiated upon AE improving to Grade 1 or less and continue to taper over at least 4 weeks.
 
2. For severe and life-threatening irAEs, IV corticosteroid should be initiated first followed by oral steroid. Other immunosuppressive treatment should be initiated if irAEs cannot be controlled by corticosteroids.
 
				
Immune-related AEs	Toxicity grade or conditions (CTCAEv4.0)	Action taken to pembrolizumab	irAE management with corticosteroid and/or other therapies	Monitor and follow-up
Pneumonitis	Grade 2	Withhold	
 
• Administer corticosteroids (initial dose of 1-2 mg/kg prednisone or equivalent) followed by taper
 
	
 
• Monitor participants for signs and symptoms of pneumonitis
 
• Evaluate participants with suspected pneumonitis with radiographic imaging and initiate corticosteroid treatment
 
• Add prophylactic antibiotics for opportunistic infections
 

	Grade 3 or 4, or recurrent Grade 2	Permanently discontinue		
Diarrhea / Colitis	Grade 2 or 3	Withhold	
 
• Administer corticosteroids (initial dose of 1-2 mg/kg prednisone or equivalent) followed by taper
 
	
 
• Monitor participants for signs and symptoms of enterocolitis (ie, diarrhea, abdominal pain, blood or mucus in stool with or without fever) and of bowel perforation (ie, peritoneal signs and ileus).
 
• Participants with <math>\geq</math> Grade 2 diarrhea suspecting colitis should consider GI consultation and performing endoscopy to rule out colitis.
 
• Participants with diarrhea/colitis should be advised to drink liberal quantities of clear fluids. If sufficient oral fluid intake is not feasible, fluid and electrolytes should be substituted via IV infusion.
 

	Grade 4	Permanently discontinue		
AST / ALT elevation or Increased bilirubin	Grade 2	Withhold	
 
• Administer corticosteroids (initial dose of 0.5- 1 mg/kg prednisone or equivalent) followed by taper
 
	
 
• Monitor with liver function tests (consider weekly or more frequently until liver enzyme value returned to baseline or is stable)
 

	Grade 3 or 4	Permanently discontinue	
 
• Administer corticosteroids (initial dose of 1-2 mg/kg prednisone or equivalent) followed by taper
 
	

Type 1 diabetes mellitus (T1DM) or Hyperglycemia	Newly onset T1DM or Grade 3 or 4 hyperglycemia associated with evidence of $\beta$ -cell failure	Withhold	
 
Initiate insulin replacement therapy for participants with T1DM
 
Administer anti-hyperglycemic in participants with hyperglycemia
 
	
 
Monitor participants for hyperglycemia or other signs and symptoms of diabetes.
 

Hypophysitis	Grade 2	Withhold	
 
Administer corticosteroids and initiate hormonal replacements as clinically indicated.
 
	
 
Monitor for signs and symptoms of hypophysitis (including hypopituitarism and adrenal insufficiency)
 

	Grade 3 or 4	Withhold or permanently discontinue 		
Hyperthyroidism	Grade 2	Continue	
 
Treat with non-selective beta-blockers (e.g., propranolol) or thionamides as appropriate
 
	
 
Monitor for signs and symptoms of thyroid disorders.
 

	Grade 3 or 4	Withhold or permanently discontinue 		
Hypothyroidism	Grade 2-4	Continue	
 
Initiate thyroid replacement hormones (eg, levothyroxine or liothyroinine) per standard of care
 
	
 
Monitor for signs and symptoms of thyroid disorders.
 

Nephritis and Renal dysfunction	Grade 2	Withhold	
 
Administer corticosteroids (prednisone 1-2 mg/kg or equivalent) followed by taper.
 
	
 
Monitor changes of renal function
 

	Grade 3 or 4	Permanently discontinue		
Myocarditis	Grade 1 or 2	Withhold	
 
Based on severity of AE administer corticosteroids
 
	
 
Ensure adequate evaluation to confirm etiology and/or exclude other causes
 

	Grade 3 or 4	Permanently discontinue		
All other immune-related AEs	Intolerable/ persistent Grade 2	Withhold	
 
Based on type and severity of AE administer corticosteroids
 
	
 
Ensure adequate evaluation to confirm etiology and/or exclude other causes
 

	Grade 3	Withhold or discontinue based on the type of event. Events that require discontinuation include and not limited to: Gullain-Barre Syndrome, encephalitis		
	Grade 4 or recurrent Grade 3	Permanently discontinue		

1. Withhold or permanently discontinue pembrolizumab is at the discretion of the investigator or treating physician.

**NOTE:**

For participants with Grade 3 or 4 immune-related endocrinopathy where withhold of pembrolizumab is required, pembrolizumab may be resumed when AE resolves to ≤ Grade 2 and is controlled with hormonal replacement therapy or achieved metabolic control (in case of T1DM).

### 5.3.2 Dose Modification for Ipilimumab

Note that ipilimumab is only used for Cycles 1-4. Therefore in the case of ipilimumab being held, Pembrolizumab may be continued if not specifically contraindicated. Aspirin may also be continued unless specifically contraindicated

**Table 3 Ipilimumab Dose Modification Guidelines for Drug-Related Adverse Events**

Toxicity	Hold For Grade	Timing for Restarting Treatment	Treatment Discontinuation
Diarrhea/Colitis	2	Toxicity resolves to Grade 0-1	Toxicity does not resolve within 12 weeks of last dose or inability to reduce corticosteroid to 10 mg or less of prednisone or equivalent per day within 12 weeks. Patients are to be treated with 1 mg/kg prednisone or equivalent if grade 2 or greater toxicity and tapered over several weeks
	3-4	Permanently discontinue	Permanently discontinue
AST, ALT, or Increased Bilirubin	2	Toxicity resolves to Grade 0-1	Toxicity does not resolve within 12 weeks of last dose
	3-4	Permanently discontinue (see exception below) a	Permanently discontinue
Type 1 diabetes mellitus (if new onset) or Hyperglycemia	T1DM or 3-4	Hold ipilimumab for new onset Type 1 diabetes mellitus or Grade 3-4 hyperglycemia associated with evidence of beta cell failure	Discontinue permanently
Hypophysitis	2-4	Toxicity resolves to Grade 0-1. Therapy with pembrolizumab can be continued while endocrine replacement therapy is instituted	Toxicity does not resolve within 12 weeks of last dose or inability to reduce corticosteroid to 10 mg or less of prednisone or equivalent per day within 12 weeks
Hyperthyroidism	3	Toxicity resolves to Grade 0-1	Toxicity does not resolve within 12 weeks of last dose or inability to reduce corticosteroid to 10 mg or less of prednisone or equivalent per day within 12 weeks
	4	Permanently discontinue	Permanently discontinue
Hypothyroidism		Therapy with ipilimumab can be continued while thyroid replacement therapy is instituted	Therapy with ipilimumab can be continued while thyroid replacement therapy is instituted
Infusion Reaction	2 b	Toxicity resolves to Grade 0-1	Permanently discontinue if toxicity develops despite adequate premedication
	3-4	Permanently discontinue	Permanently discontinue
Pneumonitis	2	Toxicity resolves to Grade 0-1	Toxicity does not resolve within 12 weeks of last dose or inability to reduce corticosteroid to 10 mg or less of prednisone or equivalent per day within 12 weeks
	3-4	Permanently discontinue	Permanently discontinue
Renal Failure or Nephritis	2	Toxicity resolves to Grade 0-1	Toxicity does not resolve within 12 weeks of last dose or inability to reduce corticosteroid to 10 mg or less of prednisone or equivalent per day within 12 weeks
	3-4	Permanently discontinue	Permanently discontinue

Toxicity	Hold For Grade	Timing for Restarting Treatment	Treatment Discontinuation
All Other Drug-Related Toxicity c	3 or Severe	Toxicity resolves to Grade 0-1	Toxicity does not resolve within 12 weeks of last dose or inability to reduce corticosteroid to 10 mg or less of prednisone or equivalent per day within 12 weeks
	4	Permanently discontinue	Permanently discontinue

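### For hypophysitis at Grades 2 to 4, Table 2 withholds (or, at Grades 3 and 4, withholds or stops) pembrolizumab while Table 3 permits it to continue, and nothing says which table prevails

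*Combined protocol and SAP*

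**What the plan says.** Section 5.3.1 governs pembrolizumab. Its lead-in is mandatory: "Pembrolizumab must be withheld for drug-related toxicities and severe or life-threatening AEs as per 3 below". Table 2 follows. Its entry for the lower grade is "Hypophysitis Grade 2 Withhold", and its entry for Grade 3 or 4 is "Withhold or permanently discontinue", with a footnote: "Withhold or permanently discontinue pembrolizumab is at the discretion of the investigator or treating physician". The management column for the same event reads "Administer corticosteroids and initiate hormonal replacements as clinically indicated". A note after Table 2 deals with Grade 3 or 4 immune-related endocrinopathy that has required a hold: "pembrolizumab may be resumed when AE resolves to ≤ Grade 2 and is controlled with hormonal replacement therapy".

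Section 5.3.2 governs ipilimumab, which is given only in cycles 1 to 4. Its opening text says that "in the case of ipilimumab being held, Pembrolizumab may be continued if not specifically contraindicated". In Table 3 the hypophysitis row lists Grades 2-4 as the grades at which ipilimumab is held. The column on restarting treatment then adds: "Therapy with pembrolizumab can be continued while endocrine replacement therapy is instituted".

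**The concern.** For the first four cycles both antibodies are given on Day 1 (Section 3.1 and Table 1), so a patient with hypophysitis in that period comes under both tables. They do not agree about pembrolizumab. A reader of Table 2 withholds it, or at the higher grades may stop it for good. A reader of Table 3 may go on giving it. The protocol has no order of precedence.

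The situation is foreseeable, because Section 1.2.2 itself describes hypophysitis as a characteristic immune-related toxicity of ipilimumab. At stake are consistent safety management of a potentially serious event and a toxicity profile (a secondary endpoint, Section 2.3.2) that does not depend on which table the investigator opened.

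**Working it through.** The plan states no figure for this point. The check is a comparison of the texts, followed by a rough size.

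**1. Pembrolizumab action by patient state**

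| Patient state | Table 2 and its note | Table 3, hypophysitis row | Result |
|---|---|---|---|
| New Grade 2 | Withhold | May continue during endocrine replacement | Conflict |
| Grade 3 or 4 | Withhold or permanently discontinue; discretion only between these two | May continue during endocrine replacement | Conflict |
| Was Grade 3 or 4, now Grade 2 or lower and controlled on replacement | Note: may resume | May continue during endocrine replacement | No conflict if the note is read as an exception to the Grade 2 row |
| Began at Grade 2, now controlled on replacement | Withhold; no resumption provision written | May continue during endocrine replacement | Conflict or gap |

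The conflict is a mandatory hold against a permission to continue, at all three grades. The last two rows show a separate asymmetry: a restart rule is written for events that began at Grade 3 or 4, and none for those that began at Grade 2.

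**2. Does anything else settle it?**

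- The opening of Section 5.3.2 allows continuation unless there is a specific contraindication. It does not define that term or name Table 2, and the Table 3 row names pembrolizumab without repeating the limit.
- The lead-in to Table 2 refers to "3 below", but the pembrolizumab table is Table 2. The cross-reference does not match, so it cannot establish precedence. If it is taken to mean Table 3, it sends a mandatory hold to the table that permits continuation.
- If pembrolizumab in the Table 3 row were a slip for ipilimumab, the row would contradict itself, because it holds ipilimumab at Grades 2-4. Either reading needs a correction.

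**3. How many patients**

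Inputs: Section 4.2.5, endocrinopathies at ipilimumab 3 mg/kg in Trial 1, gives 9 severe to life-threatening cases, all with hypopituitarism, and 12 moderate cases of mixed type. The denominator is 511, from the enterocolitis paragraph of the same section. The planned number of patients is 43.

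- Check of the denominator: 9/511 = 1.8% and 12/511 = 2.3%. Both match the percentages printed in Section 4.2.5.
- Lower figure, severe cases only: 9/511 = 1.8%; 43 × 9/511 = 0.8 patients.
- Upper figure, all moderate and severe endocrinopathies: (9 + 12)/511 = 21/511 = 4.1%; 43 × 21/511 = 1.8 patients.

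The upper figure overstates hypophysitis, since the moderate cases include thyroid disorders and Cushing's syndrome. The lower one omits an unstated number of moderate cases with hypopituitarism.

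**4. Timing against the week-12 assessment**

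Pembrolizumab is due on Day 1 of each three-week cycle, so at weeks 0, 3, 6 and 9. Section 4.2.5 gives a median onset of 2.5 months for moderate to severe endocrinopathy: 2.5 × 365.25/12 ÷ 7 = 10.9 weeks. At the median onset all four doses due before week 12 have already been scheduled.

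**The case against.** The strongest defence is that the tables can be read together. Table 3 gives permission, not an order, and Section 5.3.2 qualifies continuation by the absence of a specific contraindication. A Table 2 hold could be taken as exactly that. This part stands: a reader might infer that the protocol issues two contradictory orders, and it does not. The conflict is that one table requires a hold and the other permits dosing. It is not removed, because the qualification is undefined and the Table 3 row names pembrolizumab without it.

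A second defence is attribution: Table 2 is titled for immune-related events associated with pembrolizumab, Table 3 concerns drug-related events in the ipilimumab section, and the supportive-care guidance in Section 5.4.1 applies to events judged related to pembrolizumab. The split is plausible, but the protocol does not state it as a precedence rule, and it is hard to apply when both antibodies are given on the same day.

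Third, the note after Table 2 is not a contradiction. It covers an event that has come down from Grade 3 or 4 and is controlled on hormone replacement, whereas the Grade 2 row states an action without a restart threshold. That stands; what remains is the missing provision for events that began at Grade 2. The mismatched cross-reference is likewise editorial in itself.

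Finally, a reader might infer a threat to the primary endpoint, for instance that a patient held from cycle 2 would miss three of the four doses due before week 12. That is an extreme case, and the median onset of 2.5 months argues against it as typical. Nor is the 60% null derived from a pembrolizumab regimen: Section 8.1 bases it on reference 19, a study of nivolumab plus ipilimumab.

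**Conclusion.** The concern holds as an internal inconsistency. For hypophysitis at Grades 2 to 4 the protocol both requires pembrolizumab to be withheld (or, at Grades 3 and 4, withheld or stopped) and permits it to continue, without saying which text governs. The resumption note adds an asymmetry and the lead-in a faulty cross-reference.

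Its weight comes from being a safety instruction that cannot be applied consistently, not from its frequency. About 0.8 to 1.8 of 43 patients would be affected, on the assumption that the rate at ipilimumab 3 mg/kg carries over. It may be lower at the 1 mg/kg used here or higher with two checkpoint inhibitors; the documents give no endocrinopathy rate or onset time for this combination. With a median, half of the events come earlier, so some could precede the week-9 dose, but the effect on exposure before week 12 is probably small. Sample size, alpha and power do not depend on it. The documents do not support a claim that the week-12 response rate is materially at risk.

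**What to change.** The sponsor should reconcile five places: the lead-in to Section 5.3.1, the hypophysitis rows of Table 2, the note after Table 2, the opening text of Section 5.3.2, and the hypophysitis row of Table 3. After the edit, the pembrolizumab action for hypophysitis at each grade, including resumption for events that began at Grade 2, should be the same wherever it appears. The text should also say what counts as a specific contraindication, or which table governs when both apply.

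The table reference in the lead-in to Section 5.3.1 should be corrected. The same paragraph points to Section 5.6 for supportive care, although that guidance is in Section 5.4, and this can be corrected too.

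Which action stands is for the sponsor's clinicians; this review takes no position. The cost is amendment wording in Section 5.3, with no change to the design or the sample size.

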### 5.3.3 Dose Modification for Aspirin

Note that aspirin is known to cause GI bleeding, ulceration and hemorrhage. Any evidence of GI bleeding or ulceration based on symptoms or endoscopy should be treated as described below. For Grade 1 or 2 adverse events, patients may have proton pump inhibitor or sucralfate treatment along with aspirin.

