**Table 4 Aspirin Dose Modification Guidelines for Drug-Related Adverse Events**

Toxicity	Hold Treatment For Grade	Timing for Restarting Treatment	Treatment Discontinuation
GI Bleeding	2	Toxicity resolves to Grade 0-1	Toxicity does not resolve within 2 weeks, or continued bleeding, or life threatening or serious Grade 3 or 4 hemorrhage
	3-4	Permanently discontinue	Permanently discontinue
Renal Failure or Nephritis	2	Toxicity resolves to Grade 0-1	Toxicity does not resolve within 4 weeks
GI Ulceration	1-2	Use omeprazole or PPI or sucralfate if not currently being used	May continue aspirin if symptoms resolve with treatment
	3-4 or Severe	Toxicity resolves to Grade 1 or 0	Life threatening or serious Grade 3 or 4 toxicity

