## 5.4 Rescue Medications & Supportive Care

### 5.4.1 Supportive Care Guidelines

Subjects should receive appropriate supportive care measures as deemed necessary by the treating investigator. Suggested supportive care measures for the management of adverse events with potential immunologic etiology are outlined below. Where appropriate, these guidelines include the use of oral or intravenous treatment with corticosteroids as well as additional anti-inflammatory agents if symptoms do not improve with administration of corticosteroids. Note that several courses of steroid tapering may be necessary as symptoms may worsen when the steroid dose is decreased. For each disorder, attempts should be made to rule out other causes such as metastatic disease or bacterial or viral infection, which might require additional supportive care. The treatment guidelines are intended to be applied when the investigator determines the events to be related to pembrolizumab.

Note: if after the evaluation the event is determined not to be related, the investigator does not need to follow the treatment guidance (as outlined below). Refer to Section 5.3 for dose modification.

It may be necessary to perform conditional procedures such as bronchoscopy, endoscopy, or skin photography as part of evaluation of the event.

- **Pneumonitis:**
  - For **Grade 2 events**, treat with systemic corticosteroids. When symptoms improve to Grade 1 or less, steroid taper should be started and continued over no less than 4 weeks.
  - For **Grade 3-4 events**, immediately treat with intravenous steroids. Administer additional anti-inflammatory measures, as needed.
  - Add prophylactic antibiotics for opportunistic infections in the case of prolonged steroid administration.
- **Diarrhea/Colitis:** Subjects should be carefully monitored for signs and symptoms of enterocolitis (such as diarrhea, abdominal pain, blood or mucus in stool, with or without fever) and of bowel perforation (such as peritoneal signs and ileus).
  - All subjects who experience diarrhea/colitis should be advised to drink liberal quantities of clear fluids. If sufficient oral fluid intake is not feasible, fluid and electrolytes should be substituted via IV infusion. For Grade 2 or higher diarrhea, consider GI consultation and endoscopy to confirm or rule out colitis.
  - For **Grade 2 diarrhea/colitis**, administer oral corticosteroids.

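### Section 5.3.3 allows a PPI or sucralfate with aspirin at Grade 1 or 2 without excepting Grade 2 GI bleeding, for which Table 4 holds aspirin

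*Combined protocol and SAP*

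**What the plan says.** Section 5.3.3 warns that aspirin can cause GI bleeding, ulceration and hemorrhage. It then gives two instructions in sequence. The first covers both toxicities: "Any evidence of GI bleeding or ulceration based on symptoms or endoscopy should be treated as described below". The second is a rule by grade that does not separate them: "For Grade 1 or 2 adverse events, patients may have proton pump inhibitor or sucralfate treatment along with aspirin".

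Table 4 follows. Its second column is headed "Hold Treatment For Grade".

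- **GI bleeding.** Grade 2 stands in that column, with the restart condition "Toxicity resolves to Grade 0-1". Aspirin is discontinued if the event does not resolve within 2 weeks or bleeding continues. Grades 3-4 are permanent discontinuation. There is no entry for Grade 1.
- **GI ulceration.** Grades 1-2 stand in the same column, but the cells beside them read "Use omeprazole or PPI or sucralfate if not currently being used" and "May continue aspirin if symptoms resolve with treatment".

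Gastroprotection and continued aspirin therefore appear in the table only for ulceration, not for bleeding.

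**The concern.** The permission in the text is tied to grade alone and comes straight after a sentence that names bleeding. On its face it reaches a patient with a Grade 2 GI bleed, and the words about giving gastroprotection together with aspirin describe a patient who is still taking aspirin. Under Table 4 that patient is not taking it. A clinician who reads the paragraph and not the table could keep aspirin going under a PPI.

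Aspirin is the drug this trial adds to the ipilimumab and pembrolizumab backbone, and GI bleeding is the first serious side effect that Section 4.3.5 lists for it. The event is foreseeable here for a second reason: Sections 4.2.5 and 5.4.1 list blood in the stool among the signs of immune-mediated enterocolitis. What is at stake is patient safety and consistent dosing in a foreseeable situation.

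**Working it through.** No statistical figure is involved, so the check sets text and table side by side and then looks for a rule that ranks them.

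**Step 1: scope of the sentence.** Taken without context, Grade 1 or 2 adverse events would also include Grade 2 renal failure or nephritis, which Table 4 holds as well. The preceding sentence and the choice of co-medication limit it to GI bleeding and ulceration.

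**Step 2: comparison by event and grade.**

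| Event | Section 5.3.3 text | Table 4 | Result |
|---|---|---|---|
| GI bleeding, Grade 1 | PPI or sucralfate with aspirin allowed | no entry | no conflict |
| GI bleeding, Grade 2 | PPI or sucralfate with aspirin allowed | hold until Grade 0-1 | conflict if read literally |
| GI ulceration, Grades 1-2 | PPI or sucralfate with aspirin allowed | under the hold heading, but the cells call for gastroprotection and allow aspirin if symptoms resolve | compatible in substance; the heading and the condition need tidying |

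**Step 3: is there a precedence rule?** Three places could supply one.

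- The pointer in Section 5.3.3 to what is described below leads to both the next sentence and the table.
- Section 5.4.1 says "Refer to Section 5.3 for dose modification", which points to the whole of Section 5.3. It also sits in guidance meant for events judged related to pembrolizumab, so it says little about aspirin.
- Section 5.3.2 lets aspirin go on while ipilimumab is held, unless contraindicated. It does not address an aspirin-related bleed.

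None of them ranks the sentence against the table.

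**Step 4: what separates the two readings.** The dose in Section 5.1 is 975 mg twice daily: 2 × 975 = 1,950 mg/day, which reproduces the total in Section 1.4. With the 325 mg tablets of Section 4.3.1 that is 1,950 / 325 = 6 tablets a day. During a Grade 2 GI bleed aspirin is 0 mg/day under Table 4 and up to 1,950 mg/day if the sentence is taken as leave to continue.

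**The case against.** The best case against the point is that there is no contradiction. What the sentence permits is the co-medication. It does not tell anyone to continue aspirin or to waive a hold. Hold, restart and stop actions appear only in Table 4, which has a dedicated bleeding row, and the sentence before the permission sends the reader downward to it. The permission also matches the Grade 1-2 ulceration row so closely that it reads as a preview of that row. This is probably what the authors meant, and it is why the point is minor. It does not remove the point, because the sentence names no toxicity, follows one that names bleeding, and carries no exception.

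Two further objections stand.

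- A reader might count event-by-grade cases and report one conflict in four. That count is not robust. Grade 1-2 ulceration sits under the same hold heading as Grade 2 bleeding, and continuation there is conditional on symptom resolution. If the heading alone decides, more cases are in tension. If the cell text and context qualify it, the sentence can be qualified in the same way.
- A reader might contrast the aspirin section with Section 5.3.1, where "Pembrolizumab must be withheld for drug-related toxicities and severe or life-threatening AEs as per 3 below", and infer that the aspirin holds are optional. The documents do not support that. Section 5.3.2 has no such wording for ipilimumab either, and Table 3 still sets holds.

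Several provisions also lower the chance of harm. Section 3.3.2 excludes a history of gastritis and aspirin intolerance, Section 3.3.1 requires platelets of at least 100,000/mcL, Appendix 4 prohibits warfarin, Section 5.5.2 discourages regular NSAID use, and Section 5.6.5 requires discontinuation for unacceptable adverse experiences. None of them says what to do with aspirin at a Grade 2 bleed.

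**Conclusion.** The point holds as a minor patient-safety inconsistency. For Grade 2 GI bleeding the text of Section 5.3.3 can be read to allow aspirin with gastroprotection, Table 4 requires a hold, and the protocol does not say which governs. Letting the table row prevail reconciles them, but that step is left to the reader.

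The conclusion rests on two assumptions: that the sentence covers the two toxicities named just before it, and that the Table 4 columns are as they appear in the extracted text.

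A reader might infer that the protocol directs aspirin to continue through a Grade 2 bleed, or that patients will be harmed as a result. Neither follows. The wording is permissive, and the documents give no rate of Grade 2 GI bleeding for this combination, so the 0 against 1,950 mg/day contrast describes two readings and does not estimate harm. ORR, sample size and error rates are not affected.

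**What to change.** Replace the Grade 1 or 2 sentence in Section 5.3.3 with wording by event and grade, for example:

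> Hold aspirin for Grade 2 GI bleeding until it is back to Grade 0-1, and stop it permanently for Grade 3-4, as in Table 4. For Grade 1 GI bleeding, a PPI or sucralfate may be added to aspirin. For Grade 1-2 GI ulceration, start a PPI or sucralfate unless one is already in use; aspirin may continue provided symptoms resolve on that treatment. Table 4 governs if text and table differ.

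In Table 4, mark the Grade 1-2 ulceration row as 'no mandatory hold'. Without that mark, giving the table precedence would set the row against its own column heading. The replacement also has to keep the symptom-resolution condition, which a short permission to give gastroprotection with aspirin would drop.

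The cost is a few lines in an amendment, with no added visit, procedure or patient. The only downside is the aspirin interruption that Table 4 already requires.
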